Everolimus is a rapamycin derivative that inhibits mTORC1 through allosteric binding; it does not inhibit mTORC2 ([Efeyan 2010](#)). In the clinic, everolimus active in combination with exemestane in patients with ER+ advanced breast cancer resistant to previous hormonal deprivation therapy ([BOLERO-2 study](#); [Baselga 2012](#); [Baselga 2012](#)).

Recently, the United States Food and Drug Administration (FDA) approved palbociclib (Ibrance[®]) in combination with letrozole for the treatment of postmenopausal women with HR-positive, HER2-negative advanced breast cancer as initial endocrine-based therapy for their metastatic disease and fulvestrant in premenopausal, perimenopausal and postmenopausal women with AI refractory HR+ HER2- negative advanced breast cancer. For additional information, please refer to the Ibrance[®] Prescribing Information.

In premenopausal women who received a prior endocrine therapy within 12 months, the preferred therapy involves ovarian ablation or suppression + endocrine therapy - such as aromatase inhibitors (AIs) - as for post-menopausal patients. (NCCN Breast Cancer Guidelines, version 2.2016).

Based on the clinical benefit shown in postmenopausal patients, AIs in combination with ovarian function suppression (OFS) have been investigated in premenopausal patients with breast cancer in neoadjuvant, adjuvant and advanced settings. Results from the randomized phase III trials SOFT (Suppression of Ovarian Function Trial) and TEXT (Tamoxifen and EXemestane Trial) showed that adjuvant treatment with exemestane+OFS as compared with tamoxifen+OFS, significantly reduced recurrence in premenopausal women with HR+ early breast cancer. Results from both trials (N=5,738) showed statistically significant differences in disease free survival (DFS) at 5 years (91.1% in exemestane + OFS vs 87.3% in tamoxifen + OFS) and rate of freedom from breast cancer at 5 years (92.8% in exemestane+OFS vs 88.8% in tamoxifen+OFS) ([Pagani 2014](#)). Studies exploring the combination of third generation AIs

and goserelin in metastatic premenopausal BC patients are shown below in [Table 1-1](#). ([Montagna 2013](#))

Table 1-1 Goserelin and third generation AIs in metastatic premenopausal BC patients

Study	N	AI+goserelin (G)	ORR (CR+PR) (%)	CB (CR+PR+SD) (%)	TTP (months)	First line endocrine therapy
Forward (2014)	16	Anastrozole+G	6.2	75	N/R	No
Cheung (2010)	36	Anastrozole+G	36	67	12	Yes
	13	Exemestane+G*	N/R	38	N/R	No

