5.2 Inclusion criteria

Written informed consent must be obtained prior to study entry. Patients eligible for inclusion in this study have to meet all of the following criteria:

1. Adult men and women (≥ 18 years of age) with metastatic or locally advanced breast cancer not amenable to curative treatment by surgery or radiotherapy.
**Note: sexually active males should use a condom during intercourse while taking study treatment and for 21 days after stopping medication and should not father a child in this period. A condom is required to be used also by vasectomized men as well as during intercourse with a male partner in order to prevent delivery of the drug via seminal fluid.*
2. Histological or cytological confirmation of hormone-receptor positive (ER+ and/or PR+) breast cancer by local laboratory testing per local laboratory testing.
3. Patient has HER2-negative breast cancer (based on most recently analyzed biopsy) defined as a negative in situ hybridization test or an IHC status of 0, 1+ or 2+. If IHC is 2+, a negative in situ hybridization (FISH, CISH, or SISH) test is required by local laboratory testing.
5. A representative tumor specimen must be available for molecular testing. Newly obtained tumor biopsy specimen is required if accessible prior to entry on trial. If tissue is not accessible based on surgical evaluation, an archival tumor sample from metastatic site may be submitted.
6. Women must be postmenopausal. Postmenopausal status is defined either by:
 - Amenorrhea for at least 12 months and both follicle-stimulating hormone (FSH) and/or estradiol levels are in postmenopausal range (according to the local laboratory)
OR
 - History of bilateral oophorectomy (with or without hysterectomy) OR
 - History of partial hysterectomy with FSH and/or estradiol within post-menopausal range OR
 - Ovarian function suppressed with a GnRH agonists (negative HCG required) with estradiol levels in the postmenopausal range (according to the local laboratory)
7. Disease refractory to either, AI, tamoxifen or fulvestrant defined as:

- Recurrence while on, or within 12 months of end of adjuvant treatment with letrozole, anastrozole, exemestane, tamoxifen or fulvestrant OR
- Progression while on, or within one month of discontinuing letrozole, anastrozole, tamoxifen or fulvestrant for the treatment of locally advanced or metastatic breast cancer.

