5.3 Exclusion criteria

Patients eligible for this study must not meet any of the following criteria:

1. Patient with visceral crisis or any disease burden that makes the patient ineligible for this study per the investigator's best judgment.
2. Patients who received more than one line of chemotherapy for advanced breast cancer.

****Note: A chemotherapy line in advanced disease is an anticancer regimen(s) that contains at least 1 cytotoxic chemotherapy agent and given for greater 21 days or longer. If a cytotoxic chemotherapy regimen was discontinued for a reason other than disease progression and lasted 21 days or less, then this regimen does not count as a "prior line of chemotherapy"***

3. HER2 overexpression by local laboratory testing (IHC 3+ staining or *in situ* hybridization positive).
4. Patient has received prior treatment with anthracyclines at cumulative doses of 450 mg/m^2 or more for doxorubicin or 900 mg/m^2 or more for epirubicin.
5. Patient with a known hypersensitivity to any of the excipients of ribociclib, mTOR inhibitors, e.g. sirolimus (rapamycin), exemestane.
6. Previous treatment with mTOR inhibitors.
7. Previous treatment with exemestane for metastatic disease (except patients who received ≤ 28 days of exemestane for advanced breast cancer and did not progress).

8. Disease progression on more than one CDK 4/6 inhibitor, or have progressed more than once on the same CDK 4/6 inhibitor.
9. Patient is concurrently using other anti-cancer therapy. All anti-cancer therapy must be discontinued atleast 7 days to study treatment (C1D1). Drugs with overlapping toxicities with either everolimus or ribociclib must also be discontinued at least 7 days prior to C1D1. All AEs related to prior treatment should have resolved to CTCAE version 4.03 Grade ≤ 1 prior to study treatment (including any CDK 4/6 inhibitor).".
10. Patient has not recovered from all toxicities related to prior anticancer therapies to Grade ≤ 1 (based on NCI CTCAE version 4.03). Exception to this criterion: patients with any grade of alopecia and or neuropathy are allowed to enter the study.
11. Patient has had major surgery within 14 days prior to starting study drug or has not recovered from major side effects.
12. Patients with Child Pugh score B or C.

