6.4 Dose modification

6.4.1 Dose cohort modification

For patients who do not tolerate the protocol-specified dosing schedule, ribociclib adjustments are **recommended** in order to allow the patient to continue the study treatment.

Dose reductions are not permitted for everolimus, exemestane or GnRH agonists (if patient is currently taking). Any changes to the dose or interruption of dosing must be recorded on the Dosage Administration Record eCRF. Patients who require a study treatment hold of more than 28 days will be discontinued from the study unless discussed and approved by the sponsor ([Section 7.1.2](#)). Once dose-reduced the dose may be re-escalated once discussed and approved by the sponsor. All patients will be followed for AEs and for SAEs for 30 days following the last dose of study drug.

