6.5 Concomitant medications

6.5.1 Permitted concomitant therapy for all treatment groups

Medications required to treat AEs, manage cancer symptoms, concurrent diseases and supportive care agents, such as packed red blood cells (PRBCs), pain medications, anti-emetics, short courses of steroids, chronic use of a low dose steroid for physiologic replacement, topical treatments for stomatitis and anti-diarrheal are allowed. The use of any other potential new concomitant medications may be discussed between the investigator and the sponsor on a case by case basis.

The patient must be told to notify the investigational site about any new medications he/she takes after the start of the study drug combination. All medications (other than study drugs) and significant non-drug therapies (including vitamins, herbal medicines, physical therapy and blood transfusions) administered within 30 days of study entry and during the study must be listed on the Concomitant medications/Significant non-drug therapies eCRF.

Patients taking concomitant medication chronically should be maintained on the same dose and dose schedule throughout the study period, as medically feasible.

Refer to the ([LEE011 Investigator's Brochure](#)), ([everolimus Investigator's Brochure](#)), ([aromasin package insert](#)) and ([Appendix 1 for concomitant medications](#)).

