6.5.2 Prohibited concomitant therapy during combined ribociclib + everolimus + exemestane

The following medications are prohibited during study treatment in the study (see [Table 14-1 in Appendix 1](#), this list is not comprehensive and is only meant to be used as a guide. Please contact the medical monitor with any questions):

- Strong and moderate inhibitors or inducers of CYP3A4/5.
- Substrates of CYP3A4/5 with a narrow therapeutic index.
- Medications with a known risk for QT prolongation.
- Other investigational and anti-neoplastic therapies, including chemotherapy, immunotherapy, target therapy, biological response modifiers, or endocrine therapy other than exemestane.
- Hormone replacement therapy, topical estrogens (including any intra-vaginal preparations), megestrol acetate and selective estrogen-receptor modulators (e.g. raloxifene).
- Prolonged systemic corticosteroid treatment (≥ 2 weeks), except for topical applications (e.g. rash), inhaled sprays (e.g. obstructive airways diseases), dexamethasone mouthwash (provided by Novartis), eye drops or local injections (e.g. intraarticular) should not be given. A short duration of systemic corticosteroids is allowed (e.g. chronic obstructive pulmonary disease, LFT abnormality).
- Herbal preparations/medications (except for vitamins) or dietary supplements that are strong inhibitors or inducers of CYP3A4/5 or those with a known risk of QT prolongation,

including, but not limited to: St. John's wort, Kava, ephedra (ma huang), gingko biloba, dehydroepiandrosterone (DHEA), yohimbe, saw palmetto, black cohosh and ginseng. Patients should stop using these preparations at least 7 days prior to first dose of study treatment.

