8.3 Pregnancy

This protocol will enroll only men and post-menopausal women (chemical ovarian suppression allowed).

If a female subject, or a female partner of a male subject should become pregnant, to ensure safety, each pregnancy occurring while the patient is on study treatment must be reported to Novartis within 24 hours of learning of its occurrence. The pregnancy should be followed up to determine outcome, including spontaneous or voluntary termination, details of the birth, and the presence or absence of any birth defects, congenital abnormalities, or maternal and/or newborn complications.

Pregnancy should be recorded on a Clinical Trial Pregnancy Form and reported by the investigator to the oncology Novartis Drug Safety and Epidemiology Department (DS&E). Pregnancy follow-up should be recorded on the same form and should include an assessment of the possible relationship to the investigational treatment any pregnancy outcome. Any SAE experienced during pregnancy must be reported on the SAE Report Form. Warnings and precautions

No evidence available at the time of the approval of this study protocol indicated that special warnings or precautions were appropriate, other than those noted in the provided Investigator's Brochure for ribociclib and the approved package inserts for everolimus and exemestane. Additional safety information collected between IB updates will be communicated in the form of INs. This information will be included in the patient informed consent and should be discussed with the patient during the study as needed.

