Other investigational and antineoplastic therapies	
Other investigational therapies must not be used while the patient is on the study. Anticancer therapy (chemotherapy, hormonal therapy, including but not limited to all SERMS [including raloxifene], biologic or radiation therapy [except for palliative radiotherapy as outlined in the protocol], and surgery) other than the study treatments must not be given to patients while the patient is on the study medication. If such agents are required for a patient then the patient must discontinue study drug.
 
¹ NTI = narrow therapeutic index drugs whose exposure-response indicates that increases in their exposure levels by the concomitant use of potent inhibitors may lead to serious safety concerns (e.g., Torsades de Pointes), or drugs which have <2-fold difference in the minimum toxic concentrations and minimum effective concentrations in the blood.
 
² Herbal product
 
³ P-gp inducer
 
⁴ The list provided is as of January 2018. Check https://www.crediblemeds.org/healthcare-providers/drug-list for the most updated list.
 
As far as possible, avoid co-administration of QT prolonging drugs or any other drugs with the potential to increase the risk of drug-related QT prolongation (e.g., via a potential DDI that increases the exposure of ribociclib or the exposure of the QT prolonging drug). A definitive list of drugs with a known risk, possible risk, or conditional risk of QT prolongation and/or Torsades de Pointes (TdP) is available online at www.qtdrugs.org. Source: Novartis PK Sciences Memorandum: Drug-Drug Interactions (DDI) and Co-medication Considerations for Novartis Clinical Trials (January 2018), which is compiled from Indiana University "Clinically Relevant" Flockhart Table™, University of Washington Drug Interaction Database, and FDA Drug Development and Drug Interactions: Table of Substrates, Inhibitors and Inducers.

Table 14-2 List of medications to be used with caution during study drug treatment

Category	Drug Name
Moderate CYP3A4/5 inhibitors	Aprepitant, amprenavir, asafoetida resin (Ferula asafoetida) cimetidine, crizotinib, diltiazem, faldaprevir, imatinib, isavuconazole, netupitant, nilotinib, tofisopam, Schisandra sphenanthera (nan wu wei zi), verapamil
Moderate CYP3A4/5 inducers	Bosentan, dabrafenib, efavirenz, etravirine, genistein, modafinil, nafcillin, telotristat, lopinavir ⁵

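### The bans on endocrine, hormonal and anti-cancer therapy make no exception for the GnRH agonist that some eligible women need in order to stay postmenopausal

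*Protocol*

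**What the plan says.** Three protocol provisions treat ovarian suppression as acceptable.

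- Inclusion criterion 6 (section 5.2) accepts as postmenopausal a woman with "Ovarian function suppressed with a GnRH agonists (negative HCG required) with estradiol levels in the postmenopausal range".
- Section 8.3 states: "This protocol will enroll only men and post-menopausal women (chemical ovarian suppression allowed").
- Section 6.4.1, on dosing during the study, states: "Dose reductions are not permitted for everolimus, exemestane or GnRH agonists (if patient is currently taking").

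Section 6.5.1 adds a general rule that does not name the agonist: "Patients taking concomitant medication chronically should be maintained on the same dose and dose schedule throughout the study period, as medically feasible".

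Three other provisions bar or stop classes of treatment into which the agonist can fall.

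- Section 6.5.2 prohibits other investigational and antineoplastic therapies, "including chemotherapy, immunotherapy, target therapy, biological response modifiers, or endocrine therapy other than exemestane".
- The antineoplastic row of Table 14-1 (Appendix 1) prohibits anticancer therapy other than the study treatments and names hormonal therapy. It then says: "If such agents are required for a patient then the patient must discontinue study drug".
- Exclusion criterion 9 (section 5.3) says: "All anti-cancer therapy must be discontinued atleast 7 days to study treatment (C1D1").

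Section 7.1.4 lists use of prohibited medication among the study-specific criteria that require study treatment to be discontinued. Table 14-2 lists leuprolide, a GnRH agonist, as a caution drug because of a possible QT risk. Section 6.5.3 says caution drugs should be avoided where possible.

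**The concern.** The same woman can be eligible because of a drug and then, under another section, be barred from taking it. A site that follows Table 14-1 to the letter has to stop either the agonist or the study drug. Stopping the agonist removes the basis on which she was enrolled. It also undercuts the endocrine part of the regimen: section 1.1.2 explains that aromatase inhibitors act on non-ovarian estrogen synthesis, which is the main source only in postmenopausal women. Stopping study drug ends her treatment for a reason unrelated to toxicity or progression.

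There is a secondary safety interest in keeping suppression intact. Section 1.2.1.3 reports that ribociclib is teratogenic in the rabbit without maternal toxicity, and section 7.1.4 makes pregnancy a mandatory reason for withdrawal from treatment. Sites could also handle the same situation differently.

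**Working it through.** No figure in the plan bears on this point, so the check sets the provisions side by side.

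1. **Does the permission extend to on-study use?** Inclusion 6 governs entry. Section 8.3 allows chemical suppression without saying for how long. Section 6.4.1 decides the matter: a rule against reducing the agonist's dose in a patient who is taking it presupposes that she goes on taking it. Section 6.5.1 supports this only through its general rule on chronic medication. The permission therefore rests on inclusion 6, 6.4.1 and 8.3.

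2. **Do the bans reach the agonist?** None of the three names GnRH agonists. A drug given to keep estradiol in the postmenopausal range is, in ordinary usage, endocrine or hormonal therapy, so 6.5.2 and Table 14-1 reach it on a literal reading. Exclusion 9 reaches it only if it also counts as anti-cancer therapy, which makes exclusion 9 the weakest of the three.

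3. **Is the agonist sheltered as a study treatment?** No. Protocol section 6.1 and SAP section 2.1.1.1 both use that term for the triplet, and Table 6-1 lists no agonist.

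4. **Can an exception be inferred?** The authors wrote exceptions where they wanted them: exemestane and the dexamethasone mouthwash in 6.5.2, and palliative radiotherapy in Table 14-1. None covers the agonist.

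5. **What follows from a breach?** Table 14-1 requires study drug to stop if the barred therapy is needed, and 7.1.4 independently requires discontinuation for use of prohibited medication. The conflict therefore has an operative consequence.

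6. **Does Table 14-2 settle it?** It shows that at least one agonist was not meant to be banned. It also adds a third instruction, because 6.5.3 would have leuprolide avoided where possible and a ribociclib interruption considered if it is needed briefly. That differs both from the ban and from the assumption in 6.4.1 that the agonist continues.

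7. **How far does it extend?** Three provisions bar or stop such therapy, and none excepts the agonist. The documents do not say how many women entered by this route. SAP section 4 reports 46 + 33 = 79 phase II patients already recruited against about 66 planned. A change to exclusion 9 would now mainly correct the record, while 6.5.2 and Table 14-1 still govern women on treatment.

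**The case against.** The best defence is that no sensible site would be misled. Every operative section that names the agonist or ovarian suppression permits it, no prohibition names it, and specific text should govern general text. Section 1.1.2 words suppression as something added to endocrine therapy: "the preferred therapy involves ovarian ablation or suppression + endocrine therapy". Appendix 1 opens by permitting any medication needed for care unless it is specifically prohibited, calls its lists a guide, and refers questions to the medical monitor. Exclusion 9 can hardly be meant to stop the treatment on which inclusion 6 relies.

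Much of this stands. The intent is evidently to allow the agonist, and actual harm is unlikely. It does not remove the contradiction:

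- Appendix 1's opening rule does not help, because hormonal therapy is a named prohibited class whose row excepts only palliative radiotherapy.
- Section 1.1.2 is background and points both ways, since it also discusses LHRH agonists among hormonal therapies for male breast cancer.
- The medical monitor can explain the text but not waive it: section 12 permits no authorized deviations and requires an amendment instead.

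A reader might go further and infer that these women have no on-treatment hCG or estradiol testing and need it every cycle. The documents do not support that:

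- Table 7-1 is incomplete in the text available. The contents list allows it about five pages, and section 7.2.2.5.4 refers to HCV follow-up in the visit schedule, yet no HCV row is legible.
- SAP section 3.8.4.3 plans to list serum and urine pregnancy results, so such data are expected.
- Absence from the laboratory subsections proves little, because coagulation is scheduled in Table 7-1 without a subsection of its own.
- No provision supports a per-cycle testing frequency.

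**Conclusion.** The point holds as a low-severity contradiction between operative rules. For women who qualify through GnRH-agonist suppression, inclusion 6, 6.4.1 and 8.3 admit them and expect suppression to continue. Read literally, 6.5.2, the antineoplastic row of Table 14-1 and exclusion 9 bar or stop it, with discontinuation as the consequence under Table 14-1 and 7.1.4. The conclusion rests on reading endocrine, hormonal and anti-cancer therapy in their ordinary sense, which no operative section rules out.

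No number of patients at risk can be given. A reader might infer distortion of the primary result. The documents do not support that claim: the clinical benefit rate is analysed on the full analysis set, which keeps every patient who received the combination at least once, and nothing shows that any woman was taken off treatment for this reason. No effect on that endpoint is claimed.

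**What to change.** 1. In section 6.5.2, in the antineoplastic row of Table 14-1 and in exclusion criterion 9, add: *except GnRH agonists used for ovarian suppression in women qualifying under inclusion criterion 6, which should continue during study treatment*.
2. In section 6.5.3 and Table 14-2, note that leuprolide used for this purpose remains a caution drug because of its possible QT risk, but is not to be stopped unless suppression is maintained by other means. Without this note, the new clause would conflict with the advice to avoid caution drugs.

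The cost is one clause in three places and one note, carried by a written amendment under section 12.1. There are no added visits, samples or assays, and no change to sample size or analysis. SAP section 2.3.1 already says that the most recent prohibited list will be used, so the programmed medication list needs only to follow the amended wording.
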